20% attrition), we will have 80% power to detect an effect size of 0.31. We chose to use a highly conservative intraclass correlation to ensure sufficient power for secondary outcomes and mediation analyses (Hypothesis 2b). Thus, conservatively we will have 80% power to detect a 10 % difference in number of days using illegal opioids in the past month (e.g., 15.00 days compared to 13.5 days) and 10% difference in MCS scores (e.g., 40 compared to 36) between CHAMP and CoCM for MHS only clinics. Because these are multiple primary outcomes (and not co-primary outcomes), this power analysis assumes a Bonferroni correction for the two multiple primary outcomes. Specifically, the intervention will be interpreted to have been successful if there is a significance group different between either primary outcome, not both primary outcomes. Because of recruitment challenges, power analyses are also now provided for the lower bounds of expected enrollment. The lower-bounds power analysis assumes that we will recruit 360 study participants instead of 1200. For this lower-bounds power analysis, we assume a more realistic intraclass correlation of 0.01 instead of 0.03. Collaborative care trials conducted by [name] (MPI) and [name] (NIMH collaborator) found intraclass correlation coefficients in the range of 0.008-0.001).^{30,66} Assuming a coefficient of variation of 0.33 for the continuous outcome of days of illicit opioid use⁶⁷ and SF12V MCS scores⁶⁸, an intraclass correlation within clinics of 0.01, 12 clinics per group, 15 patients enrolled per clinic (n=288 accounting for 20% attrition), we will have 80% power to detect an effect size of 0.41. The sample size of 360 does not represent a revised enrollment target, and we will continue to enroll as many study participants as possible (up to 1,200) using enhanced recruitment methods and by extending the recruitment period if possible.

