Primary outcome. There are two primary outcomes (see Table 1). Opioid use is one of our primary outcomes and is measured using item 7E from the Brief Addiction Monitor-Revised (BAM-R) which was derived from the Addiction Severity Index35 by CESATE: “7. In the past 30 days, how many days did you use any of the following drugs: E. Opiates (e.g., Heroin, Morphine, Dilaudid, Demerol, Oxycontin, oxy, codeine (Tylenol 2,3,4), Percocet, Vicodin, fentanyl, etc.)?” Our other primary outcome is mental health related quality of life and is being measured using

the Veterans Short Form Health Survey 12 Mental Health Component Summary score (MCS). Both primary outcomes are assessed at the 6-month follow-up survey.

Secondary outcomes. This study includes 24 secondary outcomes, assessed at both the 3-month follow-up and the 6-month follow-up (Table 1). Secondary outcomes include the use of other drugs, depression, anxiety, PTSD, pain, physical health-related quality of life and perceived access to OUD care (see Table 1). Secondary outcomes also include opioid use and mental health related quality of life assessed at the 3-month follow-up survey. Exploratory outcomes are risk factors for premature mortality, including suicidal ideation, discontinuing MOUD, overdose, suicide attempts, emergency department admission, and hospitalization. Risk factors are collected via survey and adverse event reporting.

Construct/Instrument	Instrument(s)	Baseline	3-Month Follow-Up	6-Month Follow-Up
Multiple Primary Outcomes				
Opioid Use	BAM-R ^{1,2}	X	X	X
Mental health related quality of life (MCS)	Veterans Short Form-12 ³	X	X	X
Secondary Outcomes				
Pain	PEG ⁴	X	X	X
Alcohol Use	AUDIT-C ⁵	X	X	X
Cannabis Use	BAM-R ^{1,2}	X	X	X
Other Drug Use	BAM-R ^{1,2}	X	X	X
Depression	SCL-20 ⁶	X	X	X
Anxiety	PROMIS Measure - Anxiety, Short Form ^{7,8}	X	X	X
PTSD	PCL-5 ^{9,10}	X	X	X
Physical health related quality of life (PCS)	Veterans Short Form-12 ³	X	X	X
Access to Care	APAC ¹¹	X	X	X
Exploratory Outcomes				
Risk factors for mortality	WFS ¹ and Adverse Events	X	X	X
Mediator Variable				
MOUD Consistency	WFS ¹	X	X	X

APAC - Assessment of Perceived Access to Care

BAM-R - Brief Addiction Monitor-Revised

ICR - Individual Change Readiness

MOUD – Medications for Opioid Use Disorder

PCL-5 - PTSD Check List

PC-PTSD-5 – Primary Care PTSD Screen for DSM-5

PCS - Physical health related quality of life

PEG - Pain, Enjoyment of Life and General Activity

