Here the outcome measured at time t , for subject i , in clinic c is denoted by Y_{cit} . To account for the cluster-randomization this model includes a random effect for each clinic denoted as u_c . In order to allow a general longitudinal correlation and variance structure we use three subject-specific error terms denoted by u_{cit} for $t=0, 3, 6$ months. We assume a general 3×3 covariance model for these error terms to provide maximal validity to inference regarding change over time. To allow for potential non-linear change over time, we will enter time as a nominal variable by including dummy codes for the 3 and 6 month time points represented by the variables (3 months) and (6 months). Intervention main effects and interaction between intervention and time indicators capture the difference between intervention clinics and control clinics at each wave – with β_1 representing the adjusted mean difference across intervention groups at baseline (adjusting for the design variables) -- with $\beta_1 + \beta_4$ representing the adjusted mean difference across intervention groups at 3 months – and with $\beta_1 + \beta_5$ representing the adjusted mean difference across intervention groups at 6 months. Therefore, the primary contrasts are given by with β_4 as the 3-month intervention effect, and β_5 as the 6-month intervention effect. Note that each intervention effect accounts for the potential imbalance of outcomes across the intervention and control groups at baseline due to the small number of clusters (β_1) and this is removed from the cross-sectional mean contrasts at each follow-up time to define the key intervention effect parameters. *DesignVars* denotes a vector of covariates that includes: 1) low vs high fidelity, which must be controlled because it was a design/stratification variable for some clinics, and 2) additional covariates theoretically related to both the primary outcome and the probability of not completing follow-up surveys which will aid in enhancing validity against missing data and improving precision of estimation. Specifically, we will include: 1) worried about not have stable housing in the next two months, 2) being on parole or probation and/or presently awaiting charges, trial or sentencing, 3) opioid craving, 4) pain, 5) Audit-C, 6) provider trust (APAC item #6), and 7) any use of other drugs (dummy coding for each class of drug). The pre-specified primary effect of interest will be β_5 , which represents the difference in change from baseline between intervention and control clinics at 6 months. Table S2 presents a shell table for the primary outcome and Figure 2 presents a shell plot. Table S3 presents a shell table for the secondary outcomes.

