The DSMB directed the research team to discontinue consenting new patients into the trial for reasons of futility due to the current rate of recruitment. Therefore, we present a revised power analysis calculated before the outcome data are to be unmasked. The revised power analysis is based on the observed number of patients enrolled (n=254), observed number of clinics enrolling ≥ 1 patient (n=28), the observed coefficient of variation (0.97) which represents the variation in cluster sizes, and the Intraclass Correlation Coefficients (ICCs) estimated for interim analysis requested by the DSMB. For the masked interim ICC estimation we used all patient data available on 11/7/2022, including N=191 in the baseline sample and N=155 in the 6-month follow-up sample. We adjusted for treatment group and baseline primary outcomes. We used the jackknife method to compute a standard error by computing ICCs deleting each cluster in turn and then averaging these estimates.¹⁶ For the 6-month follow-up, the opioid use ICC was estimated to be 0.00 (SE= 0.02). For the 6-month follow-up, and the MCS ICC was estimated to be 0.03 (SE=0.09). Based on these estimates, and using a Bonferroni correction to account for multiple outcomes, we will have 80% power to detect a medium effect size of 0.40 for days of opioid use and a medium effect size of 0.46 for MCS. This represents a difference of 2.65 (e.g., 15.00 days compared to 12.3 days) days using opioids and a difference of 6.22 (e.g., 40 compared to 33.8) on the MCS between the intervention and control groups.

7. References

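### SAP section 6 claims 80% power on all 254 enrolled patients, with no deduction for missing 6-month outcomes, although both protocol power analyses for the effectiveness trial deduct 20%

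*SAP*

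**What the plan says.** SAP section 6 gives a revised power analysis, made after the DSMB directed that consenting stop because of slow recruitment. "The revised power analysis is based on the observed number of patients enrolled (n=254"), together with the "observed number of clinics enrolling ≥ 1 patient (n=28"), a cluster-size coefficient of variation of 0.97, and masked interim ICCs of 0.00 (SE 0.02) for opioid use and 0.03 (SE 0.09) for MCS. With a Bonferroni correction it concludes that there is "80% power to detect a medium effect size of 0.40 for days of opioid use and a medium effect size of 0.46 for MCS", equated to 2.65 days and 6.22 points. It mentions no attrition and gives no analysed N, formula or degrees of freedom.

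SAP section 3 says: "Both primary outcomes are assessed at the 6-month follow-up survey". SAP section 4.1 makes β5 the primary effect, "which represents the difference in change from baseline between intervention and control clinics at 6 months".

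Protocol section 9.2 contains two power analyses for the effectiveness trial. The main one works on 960 of 1,200 patients: "20% attrition), we will have 80% power to detect an effect size of 0.31". The lower-bound one works on 288 of 360: "15 patients enrolled per clinic (n=288 accounting for 20% attrition"), giving 0.41.

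The only follow-up counts in SAP section 6 concern the interim ICC data set, "including N=191 in the baseline sample and N=155 in the 6-month follow-up sample".

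**The concern.** Power for a 6-month contrast depends mainly on how many patients supply a 6-month outcome. Section 6 counts everyone enrolled, which amounts to assuming complete follow-up. Nothing in either document supports that assumption, and it departs without explanation from the protocol's own practice. This is the trial's current power statement, on a sample far below the 1,200 target. A non-significant result will be read against it, and a reader told that the trial had 80% power for 0.40 and 0.46 would take such a result as stronger evidence against those effects than it is.

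**Working it through.** **Inputs.** N = 254, 28 clinics (mean 254/28 = 9.07), CV 0.97, ICC 0.00 and 0.03 (SAP section 6). Two-sided alpha 0.05/2 = 0.025 (SAP section 4.1; two-tailed tests in protocol section 9.4.1). Power 80%. Equal arms are assumed. The 20% loss is the protocol's planning rate and is an assumption for these 254: 254 × 0.8 = 203.

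**Formulas.**
- Design effect: DE = 1 + [(1 + CV²) × N/28 − 1] × ICC
- Detectable effect: d = q × √(4·DE/N)
- q = 2.241 + 0.842 = 3.083 under a normal approximation, or 3.242 from the noncentral t on 28 − 2 = 26 df

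**Step 1. The SAP's figures at N = 254.**
- Opioid days, ICC 0: √(4/254) = 0.1255, so d = 0.387 (normal) to 0.407 (t). With ICC 0.004, which prints as 0.00, the normal value is 0.400.
- MCS, ICC 0.03: DE = 1 + (1.941 × 9.07 − 1) × 0.03 = 1.498, so d = 0.474 to 0.498. With ICC 0.025, which prints as 0.03, the normal value is 0.460.

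So 0.40 and 0.46 are consistent with all 254 patients to within ICC rounding, and are not shown to be wrong at that N.

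**Step 2. The protocol's practice.** With alpha 0.025, equal clusters and t on 24 − 2 = 22 df (q = 3.273):
- 960 patients, 40 per clinic, ICC 0.03: DE = 2.17, d = 0.311 (stated 0.31)
- 288 patients, 12 per clinic, ICC 0.01: DE = 1.11, d = 0.406 (stated 0.41)

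Without the deduction these would be 0.297 (1,200) and 0.368 (360). The protocol's figures therefore do rest on the 20% deduction.

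**Step 3. Change only the loss.** Accept 0.40 and 0.46 as correct at 254 and scale by the ratio of standard errors. SDs implied by the SAP are 2.65/0.40 = 6.6 days and 6.22/0.46 = 13.5 points.

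| Loss | Outcome | SE ratio | Detectable effect | Power at the stated effect |
|---|---|---|---|---|
| 20% | Opioid days | 1.119 | 0.447 (3.0 days) | 70% |
| 20% | MCS | 1.078 | 0.496 (6.7 points) | 73% |
| 10% | Opioid days | 1.054 | 0.422 | 75% |
| 10% | MCS | 1.035 | 0.476 | 77% |

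**Step 4. Recompute from the printed inputs** (normal to t on 26 df).

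| N | Opioid days | MCS (ICC 0.03) |
|---|---|---|
| 254 | 0.387–0.407 | 0.474–0.498 |
| 228.6 (10% loss) | 0.408–0.429 | 0.490–0.516 |
| 203 (20% loss) | 0.433–0.455 | 0.511–0.537 |

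At 203, power is 73% to 68% for 0.40 and 70% to 66% for 0.46. In raw units the 20% case is 2.9–3.0 days and 6.9–7.3 points. Even at ICC 0.025, MCS needs 0.498–0.524.

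**Step 5. Effect of the change contrast.** β5 is a difference in changes, so for complete data its standard error carries a factor √(2(1 − r)), where r is the baseline to 6-month correlation. Step 4 corresponds to r = 0.5 (factor 1). At N = 203, r = 0.3 gives 0.512–0.538 and 0.604–0.635, while r = 0.6 gives 0.387–0.407 and 0.457–0.480. The stated values return at r = 0.57–0.61 (opioid days) and 0.59–0.63 (MCS). Neither document gives r.

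**The case against.** The strongest reply is that the figures are right for the N stated, and that every figure after deduction rests on assumptions.

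- **The loss rate is unknown.** This stands. The interim counts give 155/191 = 0.81, but some patients may not yet have been due at 6 months, so this is not a retention rate. The 20% is the protocol's planning value.
- **Removing 20% of patients overstates the loss.** This stands in part. Maximum likelihood with an unstructured covariance uses baseline and 3-month data from patients who miss 6 months. Ignoring clustering, and with assumed correlations of 0.5 to 0.7, the effective N is about 209 to 227 rather than 203, depending on who misses what. At the favourable end, √(254/227) = 1.058 takes 0.40 to 0.42, with power about 75%. That is still short of 80%. SAP section 5 relies on missing-at-random to avoid bias; that does not recover the lost information.
- **Baseline adjustment could make up the shortfall.** It could. The interim ICCs were adjusted for baseline outcomes. If the power calculation were also baseline-adjusted (factor √(1 − r²)), r of about 0.38–0.48 and 0.43–0.52 would restore 0.40 and 0.46 at 203. But section 6 does not say this, and β5 is a change contrast, which needs the larger correlations in Step 5.
- **Attrition may have been built in silently.** With 203 patients and an uncorrected alpha of 0.05, normal-approximation power is 81% at 0.40 and about 79–80% at 0.46. That contradicts the stated N and the stated Bonferroni correction.
- **Other uncertainty is larger.** True for MCS: one SE above the estimate (ICC 0.12) gives about 0.67 at 254. The opioid outcome will also be analysed with a binomial-logit mixed model, for which a two-means formula is only approximate. Both points argue for ranges, not for omitting the loss.

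**Conclusion.** The concern holds. Section 6 supports 80% power only if all 254 patients supply a 6-month outcome, or if an unstated gain from baseline data offsets the loss. With the SAP's own figures accepted and 20% loss assumed, detectable effects are about 0.45 and 0.50, and power at the stated effects is about 70% and 73%. At 10% loss, power is about 75% and 77%. From the printed inputs at 20% loss, power is 68–73% for opioid days and 66–70% for MCS, assuming no net gain or loss of variance from β5 (r = 0.5). Use of partial data would soften these figures somewhat. The true shortfall cannot be fixed from the documents, because the 6-month loss and the baseline correlation are both missing. It does not invalidate the analysis, but the power statement should be corrected.

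**What to change.** Restate SAP section 6 on the number of patients with a 6-month outcome or, if that is not yet known, on 254 less 20% with the rate labelled as an assumption. Keep the unequal-cluster design effect and alpha 0.025. Give the formula, the degrees of freedom and the baseline to 6-month correlation assumed for β5. Unrounded ICCs would also let a reader reproduce the figures. Report the detectable effects as ranges with matching differences in days and points. The cost is SAP wording only: sample size, test, alpha and estimand do not change. The detectable effects will probably look less favourable, unless the baseline correlation is high enough to offset the loss.

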	Overall n (%) or μ (SD)	Intervention Group n (%) or μ (SD)	Control Group n (%) or μ (SD)
Age (years)			
Are you of Hispanic, Latino/a/e or Spanish origin?			
Yes			
No			
Missing			
Race			
American Indian, Alaska Native, or other Indigenous group			
Native Hawaiian or other Pacific Islander			
African American or Black			
White			
Multi-race			
Another Identity			
Missing			
Current Gender Identity			
Man			
Woman			
Non-binary or gender fluid			
Missing			
Marital Status			
Divorced			
Married or living with a partner			
Separated			
Single, never married			

Missing

Housing Status

No, not living in stable housing

Yes, living in stable housing

Missing

Concern about Future Housing

No, not worried about housing in the near future

Yes, worried about housing in the near future

Missing

Parole/Probation

No

Yes

Missing

Awaiting charges, trial, or sentencing

No

Yes

Missing

Currently mandated by a court to receive addiction treatment

No

Yes

Missing

Individual Readiness to Change (ICR; range: 0-10)

Importance for change

Confidence for change

Readiness for change

Clinical Characteristics:

Veterans Short Form 12 Mental Health Component Summary score

(MCS; range: 0-100)

Opioid Use:

Any opioid use in the past 30 days

Number of days of opioid use in the past 30 days

Opioid Craving:

Not at all

Slightly

Moderately

Considerably

Extremely

Medication for OUD:

Lifetime

Current

Alcohol Use: (AUDIT-C; range: 0-12)

Other Drug Use: Any use in the past 30 days

Cocaine and/or crack use

Other stimulant use

Sedative and/or tranquilizer use

Cannabis use

Inhalant use

Other illegal drug use

Recent Overdose Experience

Ever overdosed

Number of previous overdoses

Overdosed in the past 6 months

Number of overdoses in the past 6 months

Pain Level (PEG; range: 0-10)

Hopkins Symptoms Checklist (SCL-20; range: 0-4)

Anxiety (PROMIS Measure - Anxiety 8a - Adult v1.0: range: 36.4-76.8)

PTSD Checklist (PCL-5; range: 0-80)

Table S2. Multiple primary outcomes across intervention conditions

	Intervention		Control		Treatment Effects		
	Mean (SD)	95% CI	Mean (SD)	95% CI	Adjusted Odds Ratio	95% CI	Cohen's d
Opioid Use							
Baseline							
3 months							
6 months (primary outcome)							
					Adjusted Mean Difference	95% CI	Cohen's d
MCS							
Baseline							
3 months							
6 months (primary outcome)							

Table S3. Treatment effects for secondary and exploratory outcomes at 3 and 6 month follow-up

	Intervention				Control				Unstandardized Effects		Cohen's d	
	N	n	Mean (SD)	95% CI	n	Mean (SD)	95% CI	adj. B	p	d	95% CI	
Pain, Enjoyment of Life and General Activity - PEG												
Baseline										-	-	-
3 months										-	-	-
6 months										-	-	-
Depression – SCL-20												
Baseline										-	-	-
3 months										-	-	-
6 months										-	-	-
Anxiety – PROMIS Measure – Anxiety, 8-item Short Form												
Baseline										-	-	-
3 months										-	-	-
6 months										-	-	-
PTSD – PCL-5												
Baseline										-	-	-
3 months										-	-	-
6 months										-	-	-
Physical Health-Related Quality of Life – PCS												
Baseline										-	-	-
3 months										-	-	-

6 months

**Assessment of Perceived
Access to Care – APAC**

Baseline

3 months

6 months

	Intervention				Control				Unstandardized Effects		Adjusted Odds Ratio	
	N	n	Marginal Probability (SD)	95% CI	n	Marginal Probability (SD)	95% CI	adj. B	p	AOR	95% CI	
Alcohol Use – AUDIT-C												
Baseline												
3 months												
6 months												
Cannabis use – BAM-R												
Baseline												
3 months												
6 months												
Other illegal drugs – BAM-R												
Baseline												
3 months												
6 months												

Table S4a. Moderation analysis

	adj. B	SE	95% CI
Intervention Group			
MOUD Consistency Predicting Opioid Use			
3 months			
6 months			
MOUD Consistency Predicting MCS			
3 months			
6 months			
Control Group			
MOUD Consistency Predicting Opioid Use			
3 months			
6 months			
MOUD Consistency Predicting MCS			
3 months			
6 months			

Table S4b. Mediation analysis

	adj. B	SE	95% CI
Intervention Predicting MOUD Consistency			
3 months			
6 months			

MOUD Consistency Predicting Opioid Use

3 months

6 months

MOUD Consistency Predicting MCS

3 months

6 months

Indirect Effects

Intervention-> MOUD Consistency-> Opioid Use

3 months

6 months

Intervention-> MOUD Consistency-> MCS

3 months

6 months
